## 7.3 Study Population

## 7.3.1 Inclusion Criteria

Subjects must meet all of the following criteria to be eligible for the study:

1. Completed Protocol PRO 2018-03

OR

Protocol PRO 2018-02 and did not enroll in Protocol PRO 2018-03.

2. Men or non-pregnant or non-breastfeeding women over 21 years of age

- At PRO 2018-02 baseline visit had an overall score of very thin, or thin on the LFGS, as agreed upon by the Treating and Evaluating Investigators, and desires at least a 1-point improvement in overall LFGS score; OR
  - Had a Fitzpatrick skin phototype IV, V or VI and has an LFGS score of thick or full, as agreed upon by the Treating and Evaluating Investigators, and desires treatment to the vermilion body of 1 or both lips
- 4. If female and of childbearing potential, a negative urine pregnancy test at Visit 1/Day 1 and the subject agrees to use adequate contraception during the study period.
- 5. Willing to give written informed consent and read and sign the Adverse Event of Special Interest (AESI) letter dated 04JUN19.

#### 7.3.2 Exclusion Criteria

Subjects who meet any of the following criteria will be excluded from the study:

- 1. Women who are pregnant, lactating, or planning a pregnancy.
- 2. Subjects with a known history of allergy, anaphylaxis or hypersensitivity to injectable hyaluronic acid products, local anesthetics of the amide type such as lidocaine, or to latex.
- 3. Subjects with a significant ongoing adverse event from PRO 2018-02 or PRO 2018-03 that in the opinion of the investigator could be worsened by participation in this study.
- 4. Subjects that experienced an SAE, AESI, visual changes or other serious medical conditions during PRO 2018-02 or PRO 2018-03.
- 5. Subjects with abnormal vision evaluations (Confrontational Visual Fields, Ocular Motility) or abnormal Snellen Visual Acuity at Visit 1 pre-treatment as defined in section 7.6.5 and Appendix 5.
- 6. Subjects who are unable to withhold thrombolytics, or inhibitors of platelet aggregation or nonsteroidal anti-inflammatory drugs (NSAIDs, e.g., aspirin, ibuprofen) or other substances known to increase coagulation time (e.g., herbal supplements with garlic or gingko) within 10 days before AND after any injection session.
- 7. Subjects with clinically significant organic disease including clinically significant cardiovascular, hepatic, pulmonary, neurologic, or renal disease or other medical condition, serious intercurrent illness, or extenuating circumstance that, in the opinion of the investigator, preclude participation in the trial.
- 8. Subjects with lip tattoos, piercings, facial hair, or scars that would interfere with visualization of the lips and perioral area for the effectiveness assessments.
- 9. Subjects with abnormal lip function, with inability to effectively sip water through a straw.
- 10. Subjects with abnormal lip sensation with inability to feel a 0.4G monofilament or a cotton wisp at any site on the lip.
- 11. Subjects with moderate or severe abnormal lip asymmetry.

- 12. Subjects with any mass formation on the lip.
- 13. Subjects with dentures or any device covering all or part of the upper palate, and/or severe malocclusion or dentofacial or maxillofacial deformities as judged by the Treating Investigator. Subjects planning to undergo extensive dental procedures such as dental implants, multiple tooth extractions, or oral surgery should not participate. Minor dental procedures such as teeth cleaning and repair of caries are not exclusionary.
- 14. Subjects that have undergone facial plastic surgery or received permanent facial implants (e.g., polymethylmethacrylate, silicone, polytetrafluoroethylene, polyacrylamide, lifting threads) anywhere in the face or neck, or are planning to be implanted with any of these products during the study.
- 15. Subjects that have undergone semi-permanent dermal filler treatment (e.g., calcium hydroxylapatite, poly-L-lactic acid) in the lower face (below the orbital rim) within 12 months before enrollment or are planning to undergo such treatment during the study.
- 16. Subjects that have undergone facial tissue augmentation with fat injections, botulinum toxin injections in the lower face (below the orbital rim), mesotherapy, or cosmetic procedures in the face or neck (e.g., face-lift, laser, photo-modulation, intense pulsed light, radio frequency, dermabrasion, moderate or greater depth chemical peel, microneedling, or other ablative procedures) within 9 months before enrollment or are planning to undergo any of these procedures during the study.
- 17. that have used ANY lip filling agents within 12 months of study enrollment (hyaluronic acid products, collagen-based products, etc.) other than Investigational Device administered in PRO 2018-02 and PRO-2018-03.
- 18. Subjects that have used any lip plumping products or devices within 10 days before enrollment or are planning to use such products during the study.
- 19. Subjects that have begun using any over-the-counter (OTC) or prescription oral or topical anti-wrinkle products for the lips or around the mouth within 90 days before enrollment or are planning to begin using such products during the study (Subjects who have been on a stable regimen of such products for at least 90 days are eligible for the study and must continue their regimen throughout the study).
- 20. Subjects that have a history or presence of bleeding disorders.
- 21. Subjects that have used systemic corticosteroids or immunosuppressive medications within 30 days prior to treatment.
- 22. Subjects that are on a concurrent regimen of lidocaine or structurally related local anesthetics (e.g., bupivacaine)
- 23. Subjects that have an active inflammation (skin eruptions such as cysts, pimples, rashes, or hives), infection cancerous or precancerous lesion, or unhealed wound on the face.
- 24. Subjects that have a history of known susceptibility to keloid formation or hypertrophic scars.
- 25. Subjects that have porphyria.

- 26. Subjects that have active herpes labialias lesions at the time of injections. Subjects with a history of herpes labialis who have had four (4) or more outbreaks in the 12 months prior to enrollment are also excluded even in the absence of lesions at the baseline visit.
- 27. Subjects that have impaired cardiac conduction, severely impaired hepatic function, or severe renal dysfunction that, in the opinion of the investigator, would place them at risk of associated complications from these illnesses during the course of the study.
- 28. Subjects that have any uncontrolled disease, i.e., a condition that has not been appropriately diagnosed, evaluated, and received medically appropriate treatment or care
- 29. Subjects that have severe cardiovascular disease; examples include but are not limited to New York Heart Association heart failure classification III or IV, unstable angina, and internal pacemakers. Potential subjects with other significant cardiovascular diseases should be discussed with the Medical Monitor before enrolling.

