## 7.7.1 Visit 1/Day 1: Treatment

Visit is  $\pm 14$  days of Day 168/Month 6 telephone call for PRO 2018-03 or for subjects enrolled from PRO 2018-02, Visit 1 is Day 1.

- Obtain written informed consent and read and sign the AESI letter dated 04JUN19.
- Update the medical history and demographic information as needed from entry to Protocol PRO 2018-02 and PRO 2018-03
- Perform vital signs (temperature, heart rate, blood pressure, and respiratory rate)
- Vision evaluation (Snellen visual acuity, confrontational visual fields, ocular motility)
- Obtain/record concomitant medications/treatments

- Evaluate inclusion/exclusion criteria
- Perform urine pregnancy test for all women of childbearing potential
- Reason for study participation question
- LFGS assessment
- POL assessment
- Lip function evaluation prior to treatment administration
- Lip sensation evaluation prior to treatment administration
- Lip texture evaluation prior to treatment administration
- Lip firmness evaluation prior to treatment administration
- Lip symmetry evaluation prior to treatment administration
- Lip movement/function prior to treatment administration
- pGAI assessment prior to treatment administration
- iGAI assessment prior to treatment administration
- Swelling assessment prior to treatment administration
- Subject satisfaction with lips (VAS) prior to treatment administration
- Treatment administration waiting 15 minutes after lidocaine cream or inert cream application
- Investigator Ease of Use assessment
- Subject Pain Score immediately after treatment (VAS)
- Subject Pain Score 15 minutes after treatment (VAS)
- Vision evaluation (Snellen visual acuity, confrontational visual fields, ocular motility) 30 minutes post treatment.
- Assess AEs
- Dispense subject diary card
- Schedule next visit
- Complete CRFs

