## 7.7.2 Telephone Contacts on Day 3 and Day 14 ( $\pm$ 2 days)

- Assess AEs
- Assess concomitant medications/treatments
- Ask whether the subject is experiencing or has experienced any signs/symptoms of vision changes or stroke since the injection
- Confirm adherence to prohibited treatments/medications

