#### WARNINGS

- Defer use of *PN40082* at specific sites in which an active inflammatory process (skin eruptions such as cysts, pimples, rashes, or hives) or infection is present until the process has been controlled.
- Injection site reactions (e.g., lip swelling, lip pain, and contusion) to *PN40082*, including short-term minor or moderate inflammatory symptoms starting shortly after treatment of lips
- PN40082 must not be implanted into blood vessels. Localized superficial necrosis and scarring may occur after injection in or near vessels, such as in the lips, nose, or glabellar area. It is thought to result from the injury, obstruction, or compromise of blood vessels.
- Delayed onset inflammatory papules have been reported following the use of dermal fillers. Inflammatory papules that may occur rarely should be considered and treated as a soft tissue infection.

- Injections of 4.0 mL or greater (upper and lower lip combined) per treatment session increases the occurrence of injection site reactions. If a volume of more than 3 mL is needed to achieve optimal correction, a follow-up treatment session is recommended.
- As with all dermal filler procedures, PN40082 should not be used in vascular rich areas.
   Use of similar products in these areas, such as glabella and nose, has resulted in cases of vascular embolization and symptoms consistent with ocular vessel occlusion, such as blindness.

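### A resolved SAE, ischemic event or transient visual event arising between PRO 2018-02 and Visit 1 is left to investigator judgment, while the same event during PRO 2018-02 excludes automatically

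*Combined protocol and SAP*

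**What the plan says.** Inclusion 1 (7.3.1 and synopsis) gives two ways in. One is completion of PRO 2018-03. The other is "Protocol PRO 2018-02 and did not enroll in Protocol PRO 2018-03".

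Visit timing differs between them. Under 7.7.1 and the Schedule of Activities, a subject from PRO 2018-03 has Visit 1 within 14 days either side of the Day 168 telephone call of that study. For the other group, 7.7.1 says only that "for subjects enrolled from PRO 2018-02, Visit 1 is Day 1". No maximum time since PRO 2018-02 appears anywhere.

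Two exclusions in 7.3.2 refer to the earlier studies. Exclusion 4 removes "Subjects that experienced an SAE, AESI, visual changes or other serious medical conditions during PRO 2018-02 or PRO 2018-03". Exclusion 3 removes "Subjects with a significant ongoing adverse event from PRO 2018-02 or PRO 2018-03 that in the opinion of the investigator could be worsened" by taking part.

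Exclusion 7 has no time limit. It covers significant disease, other medical conditions, serious intercurrent illness and extenuating circumstances, but only where the investigator considers that they rule out participation. Section 7.6.3 has the medical history updated at Visit 1 for changes since Visit 1 of PRO 2018-02.

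**The concern.** Exclusion 4 is a history criterion. It turns on what the subject has experienced, not on what is found at Visit 1, and it leaves no discretion. The sponsor has therefore decided that an SAE, an AESI or a visual change after earlier filler treatment is enough to keep a subject out, even if it has cleared up.

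The criterion is tied to the period when the subject was in a study. That suits someone who passes almost directly from PRO 2018-03 into this trial. A subject who stopped after PRO 2018-02 has a stretch of time in no study, and events in that stretch are not *during* either one. The same event can then mean automatic exclusion or possible re-injection, depending only on whether the subject was still being followed when it happened.

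What is at stake is subject safety and consistent application of the sponsor's own rule, in a trial whose objective (section 6) includes the safety of repeat treatment.

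**Working it through.** No sample-size, power or error-rate figure bears on this point. The check sets the criteria side by side.

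**Length of the uncovered period before Visit 1**

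- PRO 2018-03 completers: at most about 14 days after the Day 168 call (7.7.1).
- PRO 2018-02-only subjects: no bound stated (7.3.1, 7.7.1, Schedule of Activities).

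**What happens to each kind of event**

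The table assumes that PRO 2018-02 used the AESI definition in 7.9.3.4 of this protocol (vision changes, and embolic or ischemic events). The earlier protocol is not among the documents.

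| Event | Arises during PRO 2018-02 | Arises after PRO 2018-02 and before Visit 1, PRO 2018-02-only subject |
|---|---|---|
| SAE, recovered | Excluded (no. 4) | Investigator opinion (no. 7) |
| Embolic or ischemic event, recovered | Excluded (no. 4, as AESI) | Investigator opinion (no. 7) |
| Visual event, normal examination at Visit 1 | Excluded (no. 4) | Investigator opinion (no. 7) |
| Visual change still measurable at Visit 1 | Excluded (nos. 4 and 5) | Excluded (no. 5) |
| Known hypersensitivity to hyaluronic acid filler or amide anesthetic | Excluded (no. 2) | Excluded (no. 2) |
| Lip mass, abnormal lip function or sensation, moderate or severe asymmetry, or active facial inflammation at entry | Excluded (nos. 9 to 12, 23) | Excluded (nos. 9 to 12, 23) |
| Non-serious filler reaction, resolved | Not excluded by no. 3 or 4 | Not excluded by no. 3 or 4 |

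Only the first three rows differ between the columns. All three concern events that have resolved by Visit 1.

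**Why the other criteria do not close those rows**

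- Exclusion 5 tests vision on the day. Its acuity reference is the PRO 2018-02 baseline (7.6.5.1, Appendix 5), so it spans the gap, but it detects only a change that is still there. The AESI definition includes blurred vision, double vision and pain in or around the eye, all of which can pass and leave a normal examination.
- Exclusions 9 to 12 and 23 describe present findings, and exclusion 28 describes uncontrolled disease.
- Exclusion 3 requires an event that is still ongoing and also depends on opinion.
- The history update in 7.6.3 should record such an event. Recording it does not exclude the subject.

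**Is the event asked about?**

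The telephone contacts carry a direct prompt: "Ask whether the subject is experiencing or has experienced any signs/symptoms of vision changes or stroke since the injection" (7.7.2, and again in 7.7.4 and 7.7.5). The Visit 1 list in 7.7.1 has no such prompt, so a transient event in the gap surfaces only if it comes out in the general history.

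**The case against.** The strongest answer is that the plan already handles this entry route. Exclusion 2 reaches "Subjects with a known history of allergy, anaphylaxis or hypersensitivity to injectable hyaluronic acid products" at any time. Exclusion 5 compares acuity with the PRO 2018-02 baseline. Persisting lip or facial findings exclude whenever they arose. Exclusion 3 speaks of events *from* the earlier studies, so it can be read to cover a late reaction that is still ongoing. History is updated across the whole gap, and 7.4.7 and 7.6.6 add a six-month medication and treatment review for subjects who skipped PRO 2018-03. On this view, automatic exclusion for events documented in a study, and judgment for events reported from outside one, is a reasonable choice.

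Most of this stands, and it confines the point to the first three rows of the table. It does not remove them. The protocol gives no reason for treating a resolved event differently according to whether the subject was in a study at the time. It adapted the medication review for this route and left exclusion 4 as it was.

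A second objection also stands: any interval between PRO 2018-02 and PRO 2018-03 is equally outside exclusion 4 for subjects who did roll over. Its length is not given. The contrast between routes therefore concerns the last step into this trial, and a continuous look-back would cover both intervals.

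A reader might go further and infer that late filler reactions slip through, since Appendix 2 warns that "Delayed onset inflammatory papules have been reported following the use of dermal fillers". The documents do not support that. A resolved non-serious reaction is not an AESI under 7.9.3.4, and neither exclusion 3 nor 4 would remove it even had it occurred during PRO 2018-02. The two routes treat it alike, and an active reaction with a lip mass or facial inflammation is excluded on both.

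**Conclusion.** The point holds for resolved SAEs, resolved embolic or ischemic events and transient visual events that arise between the end of PRO 2018-02 and Visit 1 in subjects who did not enroll in PRO 2018-03. For these, an automatic exclusion becomes a matter of investigator opinion. The change is worth making because it concerns subject safety and costs little. It rests on reading *during* in its ordinary sense and on the AESI definition in this protocol.

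Its size cannot be stated as a count. The protocol anticipates fewer than the 158 subjects of PRO 2018-02 but does not say how many would enter by this route, and it gives no event rate.

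Three stronger readings are not supported:

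- **An unlimited gap, or one of a year or more.** The documents state no limit, which is a different thing. Subtracting about 6 months of participation from the anticipated 20-month duration gives about 14 months, but that is the enrollment period. The gap also depends on when each subject finished PRO 2018-02, which is not given.
- **Any SAE, visual event or reaction in the gap lets the subject in.** Persisting findings and known hypersensitivity exclude, and exclusion 7 permits exclusion for the rest.
- **Bias in the evaluation of AEs by previous treatment (7.9.1).** That evaluation is descriptive, the routes already differ in treatment history, and nothing in the documents shows that this difference in screening would shift the results.

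**What to change.** Reconcile inclusion 1 (7.3.1), exclusion 4 (7.3.2) and the Visit 1 timing in 7.7.1, together with the matching synopsis text, so that the look-back in the sponsor's own exclusion 4 runs without a break to Visit 1 for both entry routes. The list of excluding events stays as the sponsor wrote it.

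Add the vision and stroke question from 7.7.2 to the Visit 1 history (7.6.3, 7.7.1), asked about the time since the last study contact. Record any such event, and any SAE or embolic or ischemic event, with dates.

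The cost is the wording of one criterion in two places, an aligned sentence in 7.7.1 and one history question that already exists in the protocol. The downside is that some PRO 2018-02-only subjects may become ineligible. Their number is probably small but cannot be estimated from the documents.

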# 7.3.3 Subject Withdrawal Criteria

A subject may withdraw from the study at any time for any reason.

A subject will be withdrawn from the study if his/her safety or well-being is determined to be at risk. Withdrawal will be made at the discretion of the investigator or at the subject's request.

A subject must withdraw from the study for any of the following reasons:

- The subject or legal representative withdraws consent
- There is a significant protocol violation as determined by the Sponsor or medical monitor.

A subject may be withdrawn from the study for any of the following reasons:

- Lost to follow-up
- Investigator discretion

Withdrawal is permanent; after a subject has been withdrawn, he/she will not be allowed to enroll again.

If a subject is withdrawn from the study for any reason, the EOS or Early Termination procedures (Visit 2/Month 1) should be completed and any outstanding data and study device should be collected. Data, including the date and primary reason for withdrawal, must be documented on the EOS case report form (CRF) and source document.

If a subject withdraws from the study at any time due to an AE, the reason for withdrawal, the nature of the AE, and its clinical course must be fully documented. The investigator must strive to follow the subject until the AE has resolved, become clinically insignificant, is stabilized, or the subject is lost to follow-up. For any SAE, follow procedures provided in Section 7.9.7.

### 7.3.4 Replacement of Subjects

A subject who withdraws from the study will not be replaced.

### 7.4 Treatments

The investigator will take responsibility for and will take all steps to maintain appropriate records and ensure appropriate supply, handling, storage, distribution, and use of study materials in accordance with the protocol and any applicable laws and regulations.

## 7.4.1 Dosage and Formulations

**Test Device:** PN40082 (manufactured by Prollenium Medical Technologies) is a clear, colorless gel in 1.0 mL pre-filled syringes with 25 mg/mL of stabilized hyaluronic acid and lidocaine 0.3% w/w. The study device will be provided by the Sponsor.

**Comparator device:** RV001 (manufactured by Prollenium Medical Technologies) is a clear, colorless gel in 1.0 mL pre-filled syringes with 25 mg/mL of stabilized hyaluronic acid to be used with LMX4, a topical lidocaine. The study device will be provided by the Sponsor. LMX4 will be provided in commercial stock packaging by the Sponsor

**Comparator device:** RV001 (manufactured by Prollenium Medical Technologies) is a clear, colorless gel in 1.0 mL pre-filled syringes with 25 mg/mL of stabilized hyaluronic acid to be used alone. The study device will be provided by the Sponsor.

#### 7.4.2 Randomization

Subjects who satisfy all of the eligibility criterial will be randomized in a 1:1:1 ratio to treatment with RV001, RV001 with a topical anesthetic or PN40082. Randomization will be performed according to a computer-generated randomization scheme that will be generated and maintained by an independent third party. A sealed copy of the randomization scheme should be retained at each site and should be available to regulatory authorities at the time of site inspection to allow for verification of the treatment identity for each subject. A unique randomization subject number will be assigned to each subject in ascending order. Each site will receive the randomization scheme.

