### 7.4.3 Study Device Administration

Subjects are physically masked (blindfolded) just prior to and during all injection procedures including the application of the LMX4 or inert cream to prevent observation of the syringes containing study device and the topical product. Any unblinded investigators and staff should be reminded NOT to discuss the treatment in the presence of the subject. Subjects will maintain the unique subject number previously assigned in Protocol PRO 2018-02 and PRO 2018-03.

The subject should be positioned in a seated position and may be reclined to as much as 45°.

Any makeup should be removed with a gentle cleanser or a specific makeup remover product (such as Neutrogena Cleansing Makeup Remover Facial Wipes).

The non-vermillion areas of the upper and lower lips should be prepared by gentle washing with a surgical scrub product (Chlorhexidine, Technicare, etc.).

To maintain the subject blinding, the upper and lower lip, upper and lower vermillion and any planned injection areas in or around the mouth corners should be covered with a liberal application of either the Sponsor provided inert cream or the topical anesthetic according to the randomization code. The designated cream product should be applied in a layer thick enough

that no skin or lip color is visible through the product. Investigators should use as much cream as necessary to achieve this result and not be limited to the contents of one tube of product.

Wait 15 minutes before treatment administration.

The anesthetic cream or inert cream should be removed by wiping firmly with a dry gauze before injecting. Only the area to be immediately treated should be wiped clear of cream. Areas not yet treated should remain covered with cream until moments prior to undergoing injection.

To prepare the syringes for use, the investigator should attach one of the needles included in the subject study device kit in a firm manner. The plunger should be gently depressed to express any unwanted air until a small droplet of implant material appears at the tip of the needle.

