## 7.4.5 Method of Packaging, Labeling, Storage, and Dispensing

For PN40082, one 1.0 mL syringe is packaged along with two fine-gauge needles (30G) in an easy-open tray. Each syringe is equipped with a Luer-Lok as well as a custom finger grip and plunger rod. The syringes contain a peelable label to be placed on the subject record for tracking purposes. Two trays are packaged in a carton. A label that includes the protocol number and Sponsor name will be attached to each carton.

For RV001 with topical anesthetic, one 1.0 mL syringe is packaged along with two fine-gauge needles (27G) in an easy-open tray. 30G fine-gauge needles will be provided in bulk by the Sponsor for use instead of the 27G needles. Each syringe is equipped with a Luer-Lok as well as a custom finger grip and plunger rod. The syringes contain a peelable label to be placed on the subject record for tracking purposes. Two trays are packaged in a carton. A label that includes the protocol number and Sponsor name will be attached to each carton. Bulk commercial supplies of LMX4 will be provided.

For RV001, one 1.0 mL syringe is packaged along with two fine-gauge needles (27G) in an easy-open tray. 30G fine-gauge needles will be provided in bulk by the Sponsor for use instead of the 27G needles. Each syringe is equipped with a Luer-Lok as well as a custom finger grip and plunger rod. The syringes contain a peelable label to be placed on the subject record for tracking purposes. Two trays are packaged in a carton. A label that includes the protocol number and Sponsor name will be attached to each carton. To confirm use of the 30G needles, the 27G needles should remain in the retained packaging for reconciliation.

All study device will be stored in a climate-controlled, limited access area.

The investigator agrees to store and administer the study device only at the site(s) listed on Form FDA 1572 (or investigator agreement/statement). The investigator, sub-investigator(s), or qualified designees also agree that the study device will be administered only to subjects who have provided written informed consent and have met all entry criteria. The study device may not be used for any purpose other than as stated in the protocol.

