## 7.4.6 Study Device Accountability

Study device will be available on site for each subject. Receipt of study device will be documented and confirmed via the Investigational Product Receipt Form. All study device must be kept in a locked area with access restricted to designated study personnel in a climate-controlled, limited access area. The administration of study device will be recorded on the Study Device Dispensing Log. The site monitor will periodically check the supply of study device held by the investigator or pharmacist to ensure accountability. At study conclusion, all unused investigational product will be returned to the Sponsor and documented using the Investigational Product Return Form.

Inventory records must be readily available for inspection by the study monitor and/or auditor, and open to inspection by regulatory authorities at any time.

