## 7.6.1 Study Roles

Each site will designate at least one Treating Investigator who is either a board certified dermatologist or board certified plastic surgeon and at least one blinded Evaluating Investigator. In addition, one or more members of the study site staff may be designated as unblinded for the purposes of assisting in the management of study device use. Any study staff designated as unblinded should have no direct contact with subjects and may not perform any subject evaluations, assessments or measurements (including vital signs, questionnaires, etc.). Designation of unblinded study staff will be recorded in the Delegation of Authorities Log form.

The Treating Investigator will be responsible for conducting the injections, ensuring that the correct randomized study device and topical product is administered in accordance with the protocol and other study instructions. Any AEs brought to the attention of the Treating Investigator will be forwarded to the blinded Evaluating Investigator for final adjudication and documentation.

The blinded Evaluating Investigator will be responsible for assigning grades for the various parameters (LFGS, POL, iGAI, lip function, lip sensation etc.). The blinded Evaluating Investigator will be responsible for recording AEs and determining their severity and relationship to the study device or the injection procedure.

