## 7.6.7 Review Inclusion/Exclusion Criteria

The inclusion and exclusion criteria will be reviewed by the investigator or qualified designee to ensure that the subject qualifies for the study.

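### Allocation concealment is not assured for the pain comparison: sites receive the scheme, and no passage says how the Treating Investigator obtains one assignment without sight of the next

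*Combined protocol and SAP*

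**What the plan says.** **Generation and custody.** Section 7.4.2 randomizes eligible subjects 1:1:1 from a computer-generated scheme that an independent third party generates and maintains. It adds that "A sealed copy of the randomization scheme should be retained at each site", so that regulators can verify treatment identity, and it ends: "A unique randomization subject number will be assigned to each subject in ascending order. Each site will receive the randomization scheme".

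**Use at the site.** Under 7.4.3 the lips are covered with "the Sponsor provided inert cream or the topical anesthetic according to the randomization code". Section 7.4.5 says "Bulk commercial supplies of LMX4 will be provided", and 7.4.6 says "Study device will be available on site for each subject". Section 7.6.1 makes the Treating Investigator responsible for "ensuring that the correct randomized study device and topical product is administered in accordance with the protocol".

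**Access.** Section 7.4.4 says that investigators, among others, will have no access to individual assignments, then has each investigator maintain the code for emergencies. Section 7.9.10.2 gives the code to each unblinded Treating Investigator.

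**Eligibility.** Section 7.6.7 reads: "The inclusion and exclusion criteria will be reviewed by the investigator or qualified designee to ensure that the subject qualifies for the study". It does not require that person to be blinded. Exclusion 13 is judged by the Treating Investigator. Inclusion 3 needs agreement between the Treating and Evaluating Investigators. Exclusions 3, 7 and 27 turn on the opinion of an unspecified investigator.

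**Order at Visit 1.** Section 2 lists randomization after eligibility review and the pre-treatment assessments, and before cream application. The 7.7.1 list has no randomization line. It goes from the pre-treatment evaluations to "Treatment administration waiting 15 minutes after lidocaine cream or inert cream application".

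**The concern.** Concealment means that whoever admits or schedules a subject cannot know which arm that subject will enter. Here the person who must know each assignment also takes part in eligibility decisions. The numbers run in ascending order and the scheme is sent to the site. Followed literally, that permits foreknowledge of the next assignment.

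The exposed result is the self-reported pain comparison, which the title and objectives name and which is the only efficacy comparison between arms stated in 8.2. Someone who can foresee the next arm could influence a borderline eligibility decision or the order of bookings. Blinding subjects and evaluators acts after assignment and does not prevent this, and no analysis can reliably remove selection at entry.

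**Working it through.** The plan gives no figure to reproduce, so the check is whether any passage closes the gap.

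1. **What must be revealed for each subject.** The site needs both the device and the cream. The two RV001 arms use the same syringe, so only the cream separates them. LMX4 is bulk stock. The carton label content named in 7.4.5 is the protocol number and Sponsor name; no subject number or assignment code is mentioned. Even if devices are supplied per subject, as 7.4.6 allows, something else at the site must say which cream to use.

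2. **Which source could reveal it.**
   - *The sealed copy.* Its stated purpose is inspection. While sealed it cannot guide treatment; once opened it could show later assignments.
   - *The scheme each site receives.* If this is the sealed copy, the working source is undescribed. If it is a second document, neither a holder nor sealing is stated.
   - *The emergency codes.* The wording of 7.9.10.2 suggests closed codes, one per subject, but they serve unblinding, not allocation.
   - *The third party.* It maintains the scheme, but no release function is described.

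3. **Whether the 7.4.4 no-access sentence closes the gap.** It cannot hold as written for the Treating Investigator, who must know what is being given (7.6.1) and who maintains the code (7.9.10.2). It could be read as covering upcoming assignments only, but it names no mechanism.

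4. **Whether the order of events closes it.** Section 2 puts eligibility review before randomization. That fixes when a subject is assigned, not whether the assignment was visible beforehand. Because Section 2 has the step, its absence from 7.7.1 is an editorial omission and not evidence about concealment.

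5. **Room for selection.** There are 5 inclusion + 29 exclusion = 34 criteria. Two give the Treating Investigator a named part (inclusion 3, exclusion 13). Three more rest on an unspecified investigator's opinion (exclusions 3, 7, 27). The thin-lip limb of inclusion 3 was set at the PRO 2018-02 baseline. The pool is limited to completers of earlier studies, is expected to be below 158, and withdrawals are not replaced (7.3.4). Entrants from PRO 2018-03 have a ±14-day window; no window is stated for those coming directly from PRO 2018-02. The Screening Log (10.2.1) records reasons for ineligibility but would not show a changed booking order.

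6. **Size.** A bias would depend on how many entries were influenced and on how far those subjects' pain scores differed from those of the subjects they displaced. The documents give neither. They also give no pre-treatment pain score, block size or stratification, so no magnitude or guessing rate can be derived.

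**The case against.** The strongest reply is that the protocol already contains most of what is asked for. Eligibility is a condition of randomization, the scheme belongs to a third party, the site copy is sealed, investigators are denied access, and the schedule has the right order. Delivery of the scheme to sites may simply mean delivery of the sealed copy. The Treating Investigator cannot satisfy inclusion 3 alone, and its second limb mixes past and present tense, so it too may have been fixed earlier. Exclusions 3, 7, 13 and 27 have no shown link to pain scores. The results are summarized descriptively, and safety of repeat injection, the other main aim, does not depend on this point in the same way.

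Much of this stands. It rules out the stronger reading a reader might take from 7.4.2, that sites work from an open list and the Treating Investigator actually sees the next assignment. No passage says so, and the wording of 7.9.10.2 points towards closed codes. It also limits the practical opportunity mainly to booking order and a few judgement-based exclusions.

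It does not supply the missing step. Each safeguard states a condition, a custodian or an intention. None describes how a single assignment, including the cream, reaches the Treating Investigator while later ones stay hidden.

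**Conclusion.** The point holds in limited form, with moderate confidence: concealment is not assured for the descriptive between-arm pain comparison. It rests on the ascending numbering, the delivery of the scheme to sites, the Treating Investigator's combined roles, and the absence of any described release mechanism. The conflict of 7.4.4 with 7.6.1 and 7.9.10.2 is plain on the text.

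A reader might infer that the pain results will be biased, or biased by some number of millimetres. The documents support neither inference. No hypothesis test, error rate or power is at stake, because none is specified. The separate SAP that Section 8 announces is not part of the document, so a release procedure described there or in a site manual would answer the point. The change is still worth making, because it is cheap and the harm it prevents cannot be repaired afterwards.

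**What to change.** Replace the last sentence of 7.4.2 with wording such as:

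> *The independent third party keeps the full scheme and releases each assignment singly, by sequentially numbered opaque sealed envelope or by phone/web, to unblinded staff, only after eligibility is documented and before cream application. Any site inspection copy stays sealed and is not used for allocation. If blocks are used, their size is not disclosed to sites.*

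Reconcile 7.4.2, 7.4.4 and 7.9.10.2 on who holds the per-subject emergency codes and who has access to assignments, so that the no-access sentence no longer contradicts the Treating Investigator's role. As an editorial change, add to 7.7.1 the randomization line already in Section 2.

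**Cost.** Fewer than 158 envelopes across five sites on the expected enrolment, plus spares, or a phone/web release by the third party already engaged. Expect some administration and a few minutes at Visit 1. No extra subjects are needed and treatment does not change. If sites already open one sealed code at a time, the change only writes that down.
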